PERSONAL SOUND AMPLIFICATION DEVICE STUDY PROTOCOL, STATISTICAL ANALYSIS PLAN, INFORMED CONSENT FORM

NCT03652909

04/07/2022

[name]
[contact]

STUDY PROTOCOL

The proposed involvement of human subjects in this research includes transportation to and from the test site for a one-time appointment. Subjects will undergo audiologic testing procedures that are similar to those encountered during routine clinical audiologic care. The proposed procedures are no more than minimal risk for the subjects.

The inclusion criteria in this study are Primarily English-speaking adults who report difficulty hearing in some daily listening situations and can follow instructions and perform study procedures. Subjects will be excluded if they cannot follow the instructions and complete the speech perception testing questionnaires.

There will be no collaborating sites where human subjects research will be performed.

Study procedures, Materials, and Potential Risks

Subjects will attend to the behavioral tasks for approximately 1-1.5 hours with breaks provided as needed. The behavioral tasks require raising a hand when soft sounds of different pitches are detected, repeating pre-recorded sentences, and providing subjective feedback. The procedures will then be repeated with the subject wearing the PSAP with prescriptive gain sound output, and the PSAP with fine-tuned sound output.

The sources of research material obtained from living human subjects are names; dates (date of birth, date of testing, etc.); test results (speech perception scores, hearing thresholds, questionnaires); and non-sensitive general and otologic health information (i.e., HIV status, substance abuse, etc. will not be recorded). Upon enrollment, each subject will be assigned a number to which identifiers, test results, and health information will be linked. Only research personnel who are directly involved with this research will have access to individually identifiable private information about human subjects. All personnel are trained and approved by the designated institution to conduct human subject research. Behavioral data will be collected by the research personnel, and data collected from the medical records will be obtained according to the procedures for requesting records through the respective medical records departments. All data collected are specifically for the proposed research project.

Data will be recorded from subjects specifically for use in this study. The auditory data recorded includes: speech perception scores, behavioral thresholds, and subjective feedback questionnaires. In addition, a data from medical chart review for risk factors, hearing loss etiology, and general information will be obtained. Each subject will be assigned a code and all data will be maintained in a protected database identified only by that code. A single copy of a list with names, codes and contact information will be kept in a locked file cabinet in the locked laboratory space designated for [name] to protect identifying information.

This study is considered to have no more than minimal risk. Patients may become bored with the testing. The test equipment and procedures to be used have been used in previous studies with human subjects with no adverse effects. All of the equipment is used in clinical settings. Loss of confidentiality is a potential risk. Procedures are in place to minimize the potential risks to make loss of confidentiality less likely. A loss of confidentiality may be considered serious risk; however, sensitive health information is not collected as data for this research, and the data collected for this research is not anticipated to cause physical, psychological, financial, or legal difficulties for subjects and/or their families.

Informed Consent and Assent

Subject recruitment and enrollment will take place at Froedtert Hospital/Medical College of Wisconsin. Planned inclusion and enrollment for this study was primarily based on the existing 'Informatics for Integrating Biology and the Bedside' (i2b2) database system. i2b2 queries EPIC medical records of patients at Froedtert Hospital/Medical College of Wisconsin. The inclusion and enrollment plan for this study was accomplished by querying i2b2 for patients with diagnosis codes including sensorineural hearing loss (SNHL) and the demographic variables in relation to the condition prevalence. Also, since the inclusion criteria includes subjects that may not have a diagnosis of SNHL or related condition, we incorporated census data to reflect the general population in our region. One of the research personnel will contact the individual either in person,

by phone, or by email. Individuals who are not directly seen in the clinic will be contacted by research personnel by phone or email. The consenting process for study participation will be performed in person. During this time the research personnel will describe the study aims, procedures, risks, and benefits. The patient will be given ample time to read and consider the consent form, and the research personnel will encourage the patient to ask questions. It will be made clear to the patient that participation in this research has no bearing on the clinical care they receive. If the patient agrees to participate, he or she will sign the IRB-approved consent form, along with the designated research personnel.

Protections Against Risk

The potential risks will be minimized as much as possible. If evidence of adverse events is noted, the reasons for these events will be identified and rectified. To protect the subjects' confidentiality, records will be kept in a secure, locked room to which only authorized individuals have access, and any electronic records (e.g., databases, spreadsheets) will be kept on password-protected computers within the investigators' locked offices and laboratories. In addition, when data from the study are presented to the public the information will not be identifiable with any of the subjects. Any data shared between MCW, UWM, and Ascending Hearing Technologies, LLC, will be securely transmitted using the same protocols in place for clinical patients. In addition, we plan to develop a secure ftp site for sharing of data.

The measures proposed to protect subjects against risk are highly likely to be effective. At MCW, data will be collected in the same area as the Otolaryngology clinic during the hours of clinic operation, and in the event of an adverse effect during any research procedure, there will be many medical professionals within close proximity of the subject.

Potential Benefits of the Proposed Research to Research Participants and Others

The primary potential benefit of the proposed research is to society, and may ultimately help individuals have improved access to sounds. Subjects will not immediately benefit as the PSAD cannot be taken home, but the more research is performed in this area and product development advances, the more likely this information will benefit those who have difficulty hearing in some daily listening situations.

Importance of the Knowledge to be Gained

The knowledge gained from this study may ultimately help subjects hear better and may help those with hearing difficulties get access to sounds. The risk to subjects is minimal, while the outcomes are expected to provide significant information relevant to evaluation and management of hearing loss, which has great potential benefit.

STATISTICAL ANALYSIS PLAN

The study design is a prospective, non-randomized, within-subjects comparison of our PSAP intervention. Given the inclusion criterion of, "adults who report having difficulty listening in some daily listening situations," we anticipated that subjects will have varied hearing thresholds across frequencies, from normal through moderate hearing loss, that may impact data analysis for the outcome measures. Therefore, the power analysis prospectively included three groups of hearing levels based on the American Speech Language Hearing Association classifications: normal hearing (≤ 25 dB HL), mild hearing loss (26-40 dB HL), and moderate hearing loss (41-55 dB HL).

The speech perception test protocol proposed for this study is the same as used by Reed et al. (2017) for their study comparing PSAP and hearing aid performance in adults with mild to moderate hearing loss.⁸ Based on the Reed et al. results comparing two types of amplification (i.e., mid-range PSAP and hearing aid), the anticipated effect size for this study was approximated at 4.3% (± 3 SD). The sample size calculation for Analysis of Variance (ANOVA) for 3 groups, effect size of 4.3, SD 3, power of .8, and alpha .05 was 11 subjects per group, for a total enrollment of 33 subjects.

Data will be analyzed using one-way repeated measures ANOVA comparing within-subject means for the conditions as defined within each primary and secondary outcome measures.

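### No-device testing always comes first, so any PSAP versus no-device comparison is confounded with test order, and no analysis can separate the two afterwards

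*Combined protocol and SAP*

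**What the plan says.** The Study Protocol's opening paragraph says that participation "includes transportation to and from the test site for a one-time appointment". Under Study procedures, Materials, and Potential Risks, the tasks are listed: "The behavioral tasks require raising a hand when soft sounds of different pitches are detected, repeating pre-recorded sentences, and providing subjective feedback". The next sentence gives the sequence: "The procedures will then be repeated with the subject wearing the PSAP with prescriptive gain sound output, and the PSAP with fine-tuned sound output". On duration, the same section says: "Subjects will attend to the behavioral tasks for approximately 1-1.5 hours with breaks provided as needed". The discussion of risks adds: "Patients may become bored with the testing".

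The Statistical Analysis Plan describes a non-randomized, within-subjects design. Its analysis statement is: "Data will be analyzed using one-way repeated measures ANOVA comparing within-subject means for the conditions", with the conditions left to the outcome definitions, which are not in the supplied text. It takes the speech test from a published study: "The speech perception test protocol proposed for this study is the same as used by" that study.

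Nowhere do the documents mention counterbalancing, a randomized test order, a practice run, a repeat no-device round or a term for test position.

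**The concern.** The protocol never uses the word unaided. But if the tasks are done once and then repeated with the device on, the first round is the no-device round, for every subject. Position 1 and no-device are then the same thing.

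Repeating sentences is plausibly open to practice, which would inflate the apparent benefit of the device. Boredom or fatigue, which the protocol itself anticipates, would hide it. Breaks may ease fatigue but do nothing about practice.

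The contrast between the two PSAP settings is less clear. Their order is given only by the way they are listed. If that order is followed for everyone, this contrast is confounded too. If the settings are alternated, it is not.

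At stake is whether a PSAP versus no-device difference can be read as a device effect at all.

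**Working it through.** **Inputs from the SAP.** Anticipated difference D = 4.3 points, SD 3, three groups, power 0.80, alpha 0.05, 11 per group, N = 33.

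**Assumed, because the documents give no value.** Within-subject correlation ρ, and drift d in points per repetition.

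**1. The plan's own figure.** For a one-way between-group ANOVA with extreme means D apart and the third midway, the noncentrality is λ = nD²/(2·SD²) = 11 × 18.49/18 = 11.3, on 2 and 30 degrees of freedom. Power is 0.824, and 11 is the smallest n that reaches 0.80. The stated sample size reproduces, but test order plays no part in it.

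**2. What can be estimated.** Take the model subject + position + condition: 33 + 2 + 2 = 37 columns.

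| Order of testing | Rank | PSAP vs no-device | Setting vs setting |
|---|---|---|---|
| Listed order for all | 35 | not estimable | not estimable |
| No-device first, PSAP settings alternated | 36 | not estimable | estimable |
| Three-sequence Latin square | 37 | estimable | estimable |

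Subject + condition alone already has rank 35, so adding position in the listed order contributes nothing. This result needs no assumption about drift or correlation.

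**3. Bias.** With linear drift and no device effect, the expected means by position are 0, d, 2d.
- Third minus first is 2d. For d = 0.5 to 1.0 this is 1.0 to 2.0 points, or 23% to 47% of 4.3.
- Average PSAP minus no-device is (d + 2d)/2 = 1.5d. This is 0.75 to 1.5 points, or 17% to 35% of 4.3, whichever setting comes first.

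**4. False positives with no device effect.** For the repeated measures F test, λ = N·Σ(μᵢ − μ̄)²/[SD²(1 − ρ)] on 2 and 64 degrees of freedom. In the listed order Σ(μᵢ − μ̄)² = 2d². At d = 0.5 and ρ = 0.5, λ = 33 × 0.5/4.5 = 3.67, and the test rejects 37% of the time.

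| Listed order | d = 0.5 | d = 0.75 | d = 1.0 |
|---|---|---|---|
| ρ = 0 | 20% | 41% | 66% |
| ρ = 0.5 | 37% | 71% | 93% |
| ρ = 0.7 | 57% | 91% | 99% |

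Smaller drift matters much less: at ρ = 0.5, d of 0.1, 0.2 or 0.25 gives about 6%, 10% or 12%. If the whole shift is a single 1-point gain after the first round, rejection is 26% at ρ = 0 and 48% at ρ = 0.5.

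Simulation at ρ = 0.5 (20,000 runs), for d = 0.5, 0.75 and 1.0:
- PSAP settings alternated: about 28%, 56% and 81%.
- Latin square with a position term: about 5% throughout.

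**5. Masking.** Take a true 1.5-point benefit of both settings, ρ = 0.5, and a decline of 0.75 per repetition. The chance of significance falls from 83% to 29% (listed order) or about 10% (settings alternated). With the Latin square and a position term it stays at 83%.

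**6. Precision after the fix.** Each condition contrast has variance 2/33 = 0.0606 of the residual variance under the Latin square, the same as without a position term. Spreading all six orders over 33 subjects gives 0.0607.

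**The case against.** **The contrast may not be a key one.** The outcome definitions are not in the supplied text, and the SAP bases its effect size on a comparison of two kinds of amplification, not amplification against none. If the main comparison is prescriptive against fine-tuned output, the stated order does not necessarily affect it. This stands as a limit on reach. Even so, three rounds are described, and no-device is very likely one of the ANOVA conditions.

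**The missing position term is not a separate fault.** Correct. Under a fixed order such a term would be useless. The order is the cause, and the term becomes useful only once the order varies.

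**Drift is assumed and may be small.** This also stands. Practice and fatigue may partly cancel, and the cited speech test protocol, which is not supplied, may set practice items or list rotation. At a drift of 0.1 to 0.25, false positives are only about 6% to 12%. At the planned 4.3-point benefit, a decline of 1.0 per repetition still leaves at least 98% power, even at ρ = 0. These points shrink the illustration but do not undo the aliasing, and the size of a 4.3-point benefit would still be misestimated.

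**No-device first is needed to set up the device.** That may hold for threshold testing. Nothing in the documents shows that it holds for the sentence tests and feedback.

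**Conclusion.** The concern holds. As written, any PSAP versus no-device contrast is fully confounded with test position, and no model fitted afterwards can separate them. That conclusion rests on the protocol's wording and the rank calculation alone.

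The direction and size of the bias are unknown. If scores drift by 0.5 to 1.0 points per repetition, with SD 3 and ρ = 0.5, false-positive rates of 37% to 93% would follow in the listed order. At drift of 0.25 or less the rate would be about 12% or lower. The setting-versus-setting contrast is affected only if the listed order is followed for everyone.

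This should be fixed rather than merely noted, because the remedy is cheap before testing and unavailable after it. Confidence is medium, mainly because the outcome definitions and the cited test protocol cannot be seen.

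**What to change.** - Keep first any no-device threshold testing needed to set the device, and prepare both PSAP settings before the sentence tests begin.
- Counterbalance the order of sentence tests and feedback across no-device, prescriptive and fine-tuned, from a list generated in advance. A three-sequence Latin square gives 11 subjects per sequence overall, split 4/4/3 within each hearing-level group of 11, with the short sequence rotated across groups. It balances position but not carryover. Using all six orders, as evenly as 11 per group allows, nearly balances carryover as well.
- State that sentence lists rotate across conditions, or cite where this is set.
- Add test position to the repeated measures model.
- If no-device testing must stay first, counterbalance the two PSAP settings and state in the SAP and the report that PSAP versus no-device differences include any order effect. If sessions have already been run in the fixed order, only that statement remains available.

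The cost is a short protocol and SAP amendment and an order list, with the same visit, tests and staff. Session logistics become somewhat harder. Some subjects will use the device before their no-device sentence test, either by sequence or because fine-tuning requires listening. The position term uses 2 of 64 error degrees of freedom, and precision is essentially unchanged.

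### The plan describes neither masking of subjects to the active PSAP setting nor a balanced order of the two settings, so the fine-tuned versus prescriptive comparison can mix the setting effect with expectation and order.

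*Combined protocol and SAP*

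**What the plan says.** The section on study procedures, materials and potential risks describes one appointment with about 1 to 1.5 hours of behavioral tasks. Subjects raise a hand to soft tones, and the remaining tasks are "repeating pre-recorded sentences, and providing subjective feedback". It continues: "The procedures will then be repeated with the subject wearing the PSAP with prescriptive gain sound output, and the PSAP with fine-tuned sound output". The first pass is, by implication, without the device. The same section lists the recorded auditory data as "speech perception scores, behavioral thresholds, and subjective feedback questionnaires", says that "Behavioral data will be collected by the research personnel", and notes that subjects may become bored.

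Under informed consent and assent, "the research personnel will describe the study aims, procedures, risks, and benefits".

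The SAP states: "The study design is a prospective, non-randomized, within-subjects comparison of our PSAP intervention". It plans a one-way repeated measures ANOVA "comparing within-subject means for the conditions as defined within each primary and secondary outcome measures", but the outcomes are not listed in the text. Total enrollment is 33.

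Nowhere do the documents mention masking, coded programs, withholding the active setting, or a randomized or counterbalanced order. The only indication of order is the sequence in which the sentence names the two settings.

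**The concern.** Both aided conditions are described as the same PSAP with a different sound output. Each subject experiences both at the same visit and gives feedback under each. A subject who knows which output is active may rate it according to what the label suggests. Tone detection and sentence repetition also depend partly on effort, though less than a rating does.

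If in addition one setting always comes second, practice, fatigue or boredom attaches to that setting. Because the comparison is within subjects, each of these influences goes straight into the mean difference under test. If label and position always coincide with setting, no later analysis can separate the three. At stake is the interpretation of any fine-tuned versus prescriptive difference, above all on the questionnaires.

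**Working it through.** **The plan's own figure.** Inputs from the SAP: 3 groups, difference 4.3, SD 3, power .8, alpha .05. I took a between-groups one-way ANOVA with two means 4.3 apart and the third midway. The noncentrality is n × (4.3/3)² / 2 = n × 2.054 / 2 = n × 1.027. At n = 11 this is 11.3 on 2 and 30 degrees of freedom, and power is 0.824. Eleven is the smallest n that reaches 0.80, so 11 per group and 33 in total are reproduced. Masking and order do not enter this calculation. It supplies only the N = 33 used below.

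**What the written design identifies.** Let δ be the true tuned-minus-prescriptive difference, e the shift due to knowing the label, and π the effect of being tested second rather than first.

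- Label known, tuned always second: every subject's expected difference is δ + e + π. There is one estimate and three unknowns.
- Label known, order balanced: subjects with tuned second give δ + e + π, and those with tuned first give δ + e − π. With a 17/16 split of 33, the mean is δ + e + π(17 − 16)/33 = δ + e + π/33. Order is nearly removed; expectation is not.
- Label withheld, order balanced: the mean is δ + π/33, to the extent that subjects cannot guess the setting.

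Masking and balancing therefore address different terms, and both are needed.

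**How sensitive a test of this size is.** Assume δ = 0 and a total shift of b SDs of the paired difference. The documents give no SD for the ratings or for paired differences, so b is an assumption. A two-sided .05 paired t-test has n − 1 degrees of freedom and noncentrality b√n. For n = 33, √33 = 5.745.

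| b (assumed) | Noncentrality, n = 33 | P(significant), n = 33 | P(significant), n = 11 |
|---|---|---|---|
| 0.2 | 1.149 | 0.200 | 0.092 |
| 0.3 | 1.723 | 0.387 | 0.147 |
| 0.5 | 2.872 | 0.795 | 0.323 |

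Without a shift each probability is 0.05. The n = 11 column is one hearing-level group. The test is two-sided, so a shift in either direction gives the same values.

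The SAP plans a repeated measures ANOVA rather than a paired t-test. With only the two settings in the model the two are equivalent (F = t²). If the first pass is included as a third condition, the overall F also reflects aided versus unaided differences, and the table then applies only to the paired contrast between the settings.

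**The case against.** The strongest reply is that the documents are silent rather than explicit. A reader might infer that subjects are told which output they are wearing and that the settings are run openly. The text does not say so. The sentence on the two outputs names the conditions for the protocol's reader. Describing aims and procedures at consent is not the same as announcing the active setting, and the consent pages are not part of the text reviewed. This stands: the point is that no masking is described, not that subjects are known to be unmasked.

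A reader might also infer that the bias favors the fine-tuned output. That is plausible for expectation but undocumented. Boredom or fatigue could work against whichever setting comes later, and the text does not firmly fix the order of the two settings. Nor are the questionnaires named as an outcome. They are recorded data, and the only measure tied to the sample size is speech perception.

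The remedy's feasibility is also open to challenge. The documents do not describe fine-tuning. If it relies on the subject's response to the scored prescriptive run, moving it earlier changes the sequence, and subjects may recognize the result. The tester would also remain unmasked and could give cues. These are real limits on the remedy. They do not remove the gap, because masking and order are procedures that a protocol should specify.

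Finally, any shift of the assumed size gives these rejection rates in any paired test of 33 subjects. That is correct: the table shows sensitivity and is not evidence that bias exists here.

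**Conclusion.** The point holds in this form. Subjective feedback and effort-dependent tests are repeated under two outputs of one device at one visit, in a non-randomized within-subject design, with no masking and no order control described. Followed as written, the fine-tuned versus prescriptive contrast can carry expectation and order effects that the planned ANOVA cannot separate from the setting effect. Direction and size are unknown.

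The figures of about 20%, 39% and 80% rest on three assumptions: no true difference, total shifts of 0.2, 0.3 and 0.5 SD of the paired difference, and a two-sided .05 paired test in all 33 subjects. They should not be read as estimates for this study. The conclusion does not extend to claiming that subjects are knowingly unmasked, that the tuned setting is favored, or that the sample size is wrong.

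**What to change.** Where the fine-tuning procedure allows:

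1. Finish tuning before any aided scoring.
2. Store the two outputs as coded programs.
3. Run them in a balanced order from a pre-prepared list.
4. Do not tell the subject which program is active until all questionnaires are complete.

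If tuning depends on the scored prescriptive run so that this is not possible, say so, and report the subjective comparison as unmasked and in fixed order.

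The cost is a short protocol paragraph and a coded list; the steps themselves call for no extra visit or staff. The downsides should be stated as limits: tuning must precede scoring, some subjects may guess the setting, the tester remains unmasked, and the unaided condition cannot be masked.
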